9.0 RECORDS

Research data will be recorded in an electronic database using a unique study ID for each patient to assure patient confidentiality. Subjects will not be referred to by this number, by name, or by any other individual identifier in any publication or external presentation. The medical records department affiliated with our institution maintains all original inpatient and outpatient chart documents. Data from source documents are used to compile the study's electronic database. Source documents are documents where patient data are recorded and documented for the first time. They include, but are not limited to, hospital records, clinical and office charts, laboratory notes, memoranda, quality of life assessments, pharmacy dispensing records, recorded data from automated instruments, copies of transcriptions that are certified after verification as being accurate and complete, and imaging. The licensed medical records department, affiliated with the institution where the patient receives medical care, maintains all original inpatient and outpatient chart documents. Patient research files are maintained by a designated research coordinator and kept in a locked room with access restricted to personnel authorized by the Clinical Research Division. Access to the database will be restricted by electronic password protection and restricted access to computers (i.e., locked offices).

10.0 PROTOCOL ENROLLMENT AND SPECIAL CONSIDERATIONS

All eligible patients will be included in this study without regard to gender or ethnicity. The incidence of AML is slightly higher in men [2], so it is expected that the distribution of these patients will reflect a slight male predominance of the disease as well as the general demographic distribution of AML patients seen at our institution. Based on our statistical approach, we will require no more than 41 patients treated at the MTD to compare with patients treated historically at our institution with GCLAM. The number of patients to be included in this trial depends on the number of dosing levels tested in Phase 1. The following accrual guidelines reflect the assumption that dosing Level 1 will be safe, and thus n=41 is assumed. If further dosing levels are required and n=12 patients enroll at dose level 1, dose level -1, and dose level -2, enrollment may occur up to 41+12+12 = 65.

ETHNIC AND GENDER DISTRIBUTION CHART						
TARGETED / PLANNED ENROLLMENT: Number of Subjects = 41						
Ethnia Catagory	Sex / Gender					
	Females	Males	Total			
Hispanic or Latino	1	2	3			
Not Hispanic or Latino	18	20	38			
Ethnic Category Total of All	19	22	41			
Racial Categories						
American Indian / Alaska Native	1 .	2	3			
Asian	1	1	2			
Native Hawaiian or Other Pacific	0	0	0			
Black or African American	1	1	2			
White	16	18	34			
Racial Categories: Total of All	19	22	41			

Projected Target Accrual ETHNIC AND GENDER DISTRIBUTION CHART

11.0 GUIDELINES FOR SERIOUS ADVERSE EVENT REPORTING

11.1 Expedited Reporting Requirements and Reporting Period

In accordance with Fred Hutch/UW Cancer Consortium IRB policy, all adverse events (AEs; whether occurring on-site or off-site), which in the opinion of the principal investigator are (1) unexpected, and (2) related or possibly related to the research, and (3) serious or suggests that the research places research participants or others at a greater risk of physical or psychological harm than was previously known or recognized, will be submitted to the IRB within ten (10) calendar days of learning of the problem. Both the "Expedited Reporting Form for Unanticipated Problems or Noncompliance" and the "Adverse Event Reporting Form", or equivalent forms, will be completed for this reporting. AEs will be monitored from the time of initial drug delivery. Upon completion of induction chemotherapy (1-2 cycles), patients will be monitored for late toxicities for 1 month or until additional anti-AML therapy is given off of this protocol.

11.2 Definitions: according to ICH guidelines and 21 CFR 312.32, IND Safety Reports, and ICH E2A,Definitions and Standards for Expedited Reporting, and adverse event is defined as follows:

- 11.2.1 Adverse Event (AE): Any untoward medical occurrence in a clinical investigation subject administered a medicinal product and which does not necessarily have a causal relationship with this treatment. An AE can therefore be any unfavorable and unintended sign (including an abnormal laboratory finding), symptom, or disease temporarily associated with the use of a medicinal product, whether or not considered related to the medicinal product. Abnormal laboratory values should not be recorded as an AE unless an intervention is required (repeating testing to confirm the abnormality is not considered an intervention), the laboratory abnormality results in a serious adverse event, or the AE results in study termination or interruption / discontinuation of study treatment. Otherwise, grade \geq 3 AEs other than hematologic toxicities will be recorded, graded, and reported as appropriate. While grade ≥ 3 hematolgoic AEs are anticipated and are thus not recorded, we will record duration of cytopenias as well as episodes of febrile neutropenia. If the degree and duration of cytopenias is consistent with significant bone marrow toxicity as defined in 8.3.3, this will be reported as an AE (and as a DLT). Medical conditions present at screening before treatment is administered are not AEs and should not be recorded. On the other hand, pre-existing medical conditions that worsen during treatment or in the post-treatment period will be recorded.
- **11.2.2** Related or Possibly Related AE: An AE is "related or possibly related to the research procedures" if in the opinion of the principal investigator, it was more likely than not caused by the research procedures. AEs that are solely caused by an underlying disease, disorder or condition of the subject or by other circumstances unrelated to either the research or any underlying disease, disorder or condition of the subject. If there is any question whether or not an AE is related or possibly related, the AE should be reported.
- 11.2.3 Serious AE (SAE): An adverse event that results in any of the following outcomes:

- Death
- Life-threatening adverse event (real risk of dying)
- Prolongation of hospitalization*
- Persistent or significant disability/incapacity/or change in psychosocial status
- Congenital anomaly
- Requirement of intervention to prevent permanent impairment of damage

*Hospitalization itself will not be considered a serious adverse event if required for complications of AML or comorbid conditions. Hospitalization will be considered a SAE if it fulfills the criteria for a serious and unexpected adverse event as otherwise described.

11.2.4 Unexpected AE: An AE is "unexpected" when its nature, severity, or frequency are not consistent with (a) the known of foreseeable risk of adverse events associated with the research procedures described in the protocol-related documents, such as the IRB-approved research protocol, informed consent document, and other relevant sources of information such as product labeling and package inserts; and are also not consistent with (b) the characteristics of the subject population being studied including the expected natural progression of any underlying disease, disorder or condition or any predisposing risk factor prolife for the adverse event.

11.3 Monitoring Adverse Events and Recording Period:

All non-hematologic grade 3-4 AEs and all grade 5 AEs starting at the time of initial drug delivery will be recorded. While grade 3-4 hematologic toxicities are anticipated, we will record duration of cytopenias as well as episodes of febrile neutropenia. Upon completion of induction chemotherapy (1-2 cycles), patients will be monitored for late toxicities/complications for 1 month or until additional anti-AML therapy is given off of this protocol.

All AEs will be assessed by the investigator or qualified designee and recorded in the electronic database. When applicable AEs should be recorded as diagnoses rather than as the individual signs and symptoms. AEs that do not meet the requirement for expedited reporting will be reported to the IRB as part of the annual renewal of the protocol. Myelosuppression and associated complications are expected events during leukemia therapy; therefore, myelosuppression and associated simple complications such as fever, infections, bleeding, and related hospitalizations will not be reported as individual AE but will be summarized in the annual report to the IRB. For example, 1) simple febrile neutropenia with hospitalization is not an expedited reportable event to the IRB but will be included in the annual report to the IRB, whereas febrile neutropenia complicated by Gram-negative bacteremia with shock or its complications is to be reported expeditiously; 2) thrombocytopenic epistaxis or bleeding from mucosal surfaces easily managed with platelet support is not an expedited reportable event to the IRB, whereas major gastrointestinal bleed will be reported expeditiously.

11.4 Recording Adverse Events:

The following information should be recorded: description of the AE, whether the AE is serious, the start and stop date of the event, the severity (grade), a description of potential relatedness of the event to a study drug or other cause, action taken due to the AE, and outcome

of the AE. Subjects who terminate the study will be followed for AEs for 1 month or until additional anti-AML therapy is given, as per section 8.4.

11.5 Grading Adverse Event Severity

All AEs will be graded in severity according to the NCI Common Terminology Criteria for Adverse Events (CTCAE) Version 4.0. as per section 8.2. If a CTCAE criterion does not exist, the investigator should use the grade or adjectives: Grade 1 (mild), Grade 2 (moderate), Grade 3 (severe), Grade 4 (life-threatening), or Grade 5 (fatal) to describe the maximum intensity of the AE.

11.6 Attribution of an Adverse Event

Association or relatedness to the study agents will be assessed by the investigator as follows:

- Definite: The event follows a reasonable temporal sequence from exposure to the investigational agent, has been previously described in association with the investigational agent, and cannot reasonably be attributed to other factors such as the subject's clinical state, other therapeutic interventions or concomitant medications; AND the event disappears or improves with withdrawal of the investigational agent and/or re-appears on re-exposure (e.g., in the event of an infusion reaction).
- Probable: The event follows a reasonable temporal sequence from exposure to the investigational agent and has been previously been described in association with the investigational agent OR cannot reasonably be attributed to other factors such as the subject's clinical state, other therapeutic interventions or concomitant medications.
- Possible: The event follows a reasonable temporal sequence from exposure to the investigational agent, but could be attributable to other factors such as the subject's clinical state, other therapeutic interventions or concomitant medications.
- Unlikely: Toxicity is doubtfully related to the investigational agent(s). The event may be attributable to other factors such as the subject's clinical state, other therapeutic interventions or concomitant medications.
- Unrelated: The event is clearly related to other factors such as the subject's clinical state, other therapeutic interventions or concomitant medications.

For general AE assessment, an AE is considered related if it is assessed as definitely, probably, or possibly related; unrelated if it is assessed as unlikely related or unrelated.

12.0. DATA AND SAFETY MONITORING PLAN

Institutional support of trial monitoring will be in accordance with the Fred Hutch / University of Washington Cancer Consortium Institutional Data and Safety Monitoring Plan (DSMP). Under the provisions of this plan, Fred Hutch Clinical Research Support coordinates data and compliance monitoring conducted by consultants, contract research organizations, or Fred Hutch employees unaffiliated with the conduct of the study. Independent monitoring visits occur at specified intervals determined by the assessed risk level of the study and the findings of previous visits per the institutional DSMP. In addition, protocols are reviewed at least annually and as needed by the Consortium Data and Safety Monitoring Committee (DSMC), Fred Hutch Scientific Review Committee (SRC) and the Fred Hutch / University of Washington Cancer Consortium Institutional Review Board (IRB). This trial will be monitored twice yearly. The

DSMC will monitor the trial yearly, and a Data and Safety Monitoring Board (DSMB) will be established to review the trial yearly as well. DSMB reviews will be offset from DSMC reviews such that the trial will be monitored twice annually. The review committees evaluate accrual, adverse events, stopping rules, and adherence to the applicable DSMP for studies actively enrolling or treating patients. The IRB reviews the study progress and safety information to assess continued acceptability of the risk-benefit ratio for human subjects. Approval of committees as applicable is necessary to continue the study. The trial will comply with the standard guidelines set forth by these regulatory committees and other institutional, state, and federal guidelines.

13.0 ETHICAL AND REGULATORY CONSIDERATIONS

13.1 Institutional Review Board

In accordance with federal regulations (21 CFR 312.66), an Institutional Review Board (IRB) that complies with regulations in 21 CFR 56 must review and approve this protocol and the informed consent form prior to initiation of the study.

13.2 Consent

The Principal Investigator or his designee must explain verbally and in writing the nature, duration, and purpose of the study and possible consequences of treatment. Patients must also be informed that they may withdraw from the study at any time and for any reason without jeopardizing their future treatment. In accordance with federal regulations (21 CFR 50), all patients enrolled in the study must sign the IRB-approved consent form.

13.3 Confidentiality

Patient medical information obtained for the purposes of this study is confidential, and disclosure to third parties, other than those noted below, is prohibited. Upon the patient's request and written permission, medical information may be given to his/her personal physician or other appropriate medical personnel responsible for the patient's welfare. Data generated for this study must be available for inspection on request to representatives of the national or local health authorities, and the associated IRB/IEC. Release of research results or data that reveal patient names or other identifiers, such as photographs, audio or videotapes, must be carried out in accordance with Department of Health and Human Services Final Standards for Privacy of Individual Health Information, 45 CFR 164.508. Written authorization must be obtained from the patient and IRB/IEC prior to the release of such information. Identifiable patient data may not be used for purposes of promoting any drugs used in this trial.

13.4 Publication Statement

The results of this clinical trial may be used for public dissemination in the form of papers, abstracts, posters, or other informational materials to be presented at scientific meetings, or published in professional journals, or as a part of an academic thesis by an investigator. Identifiable patient data may not be used for any of these presentations, manuscripts, or reports unless directed by law.

14.0 STATISTICAL CONSIDERATIONS

14.1 General Considerations:

- 14.1.1 DLTs are defined in Section 8.3. Only DLTs occurring during Cycle 1 will be used to guide dose escalation.
- 14.1.2 Patients will be considered evaluable for DLT if they received at least 75% of the assigned decitabine and G-CLAM doses during Cycle 1 or if they developed a DLT. If a patient does not develop a DLT but does not receive at least 75% of treatment during Cycle 1, the patient will be considered not evaluable for DLT and will be replaced.
- 14.1.3 Maximum tolerated dose (MTD) is defined as the highest dose studied in which the incidence of DLT is <33%.

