6.6 Assessment for Response after First Induction Course

A bone marrow aspirate should be obtained upon blood count recovery (i.e. ANC >1,000/ μ L and platelet count >100,000/ μ L) or between Days +25 to +35 after start of G-CLAM chemotherapy, whichever occurs first; a bone marrow biopsy should be obtained if spicules are absent from the aspirate sample. In patients with unclear response status, the bone marrow examination should be repeated every 7-10 days until the response can be assessed or until Day +45.

- **6.6.1** Patients achieving MRDneg CR: Patients are eligible for consolidation chemotherapy, as described in section 6.8.
- **6.6.2** Patients achieving CR with MRD, CRi, or those with persistent disease: patients are eligible for a second course of induction chemotherapy consisting of G-CLAM without decitabine provided all non-hematologic toxicities have resolved

to Grade <2. For patients who experienced \geq Grade 3 non-hematologic / noninfectious toxicity during the first induction, a dose reduction is recommended as described in section 6.7. Patients who achieve CR or CRi after a second induction are eligible to receive consolidation chemotherapy, as described in section 6.8.

6.6.3 Patients with persistent aplasia without evidence of disease after Day +45: patients will be removed from protocol.

6.7 Dose Modifications of Chemotherapeutic Drugs for Initial and Subsequent Treatment Cycles

The following dose modifications are suggested both for induction cycle #1 (i.e. if organ function parameters worsen between baseline and start of chemotherapy) and subsequent treatment cycles:

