8.0 EVALUATION AND END POINT DEFINITIONS

8.1 Treatment Response and Outcome

Treatment response (e.g. morphologic / cytogenetic / molecular complete remission, partial remission) or treatment failure (e.g. resistant disease, aplasia, morphological or molecular / cytogenetic relapse) as well as treatment outcome (e.g. overall survival, relapse-free survival, event-free survival, and remission duration) are categorized according to criteria recommended by International Working Groups [21, 33]. Patients are routinely assessed for the presence of

measurable residual disease (MRD) as detected by multiparameter flow cytometry, as per institutional practice.

8.2 Toxicity Criteria

This study will use the CTCAE (NCI Common Terminology Criteria for Adverse Events) Version 4.0 for Toxicity and Adverse Event reporting. A copy of the CTCAE v4.0 can be downloaded from the CTEP home page (http://ctep.cancer.gov).

8.3 Definition of Dose-limiting Toxicities (DLTs)

Reported adverse events and potential risks for decitabince, G-CSF, cladribine, cytarabine, and mitoxantrone are described in section 7. Dose-limiting toxicities (DLTs) used for trial monitoring are defined as follows:

- **8.3.1** Any Grade 3 non-hematologic toxicity lasting >48 hours that results in >7 day delay of the subsequent treatment cycle, with the exception of febrile neutropenia or infection.
- **8.3.2** Any Grade ≥ 4 non-hematologic toxicity, with the exception of febrile neutropenia/infection unless felt to be a direct consequence of treatment-related toxicity (e.g., intenstinal infection following mucosal barrier breakdown), and with the exception of constitutional symptoms if recovery to Grade ≤ 2 within 14 days.
- **8.3.3** Lack of recovery of ANC to $\geq 500/\mu$ L and lack of self-sustained platelet count $\geq 50,000/\mu$ L by treatment day +49 with no evidence of residual leukemia.

8.4 **Duration of Follow-up**

After removal from protocol, patients will be monitored for late toxicities/complications for 1 month or until additional anti-AML therapy is given. Patients will be followed after completion of study treatment to determine disease-free survival (for patients achieving CR or CRi) as well as event-free and overall survival (for all patients), for a maximum of 5 years. Follow-up may include periodic (e.g. every 3 months) review of medical records, and, if absolutely necessary, direct contact of the study participant.

8.5 Study Endpoints

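### DLT evaluability depends on dose received alone, so a patient with unrecovered counts who starts new therapy, or dies of an exempt infection, before Day +49 stays in the denominator as a non-DLT

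*Combined protocol and SAP*

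**What the plan says.** - **Evaluability (14.1.2).** "Patients will be considered evaluable for DLT if they received at least 75% of the assigned decitabine and G-CLAM doses during Cycle 1"; having a DLT also suffices. For a patient with neither, "the patient will be considered not evaluable for DLT and will be replaced". No length of observation is required.
- **DLT window (14.1.1).** "Only DLTs occurring during Cycle 1 will be used to guide dose escalation". The length of Cycle 1 in days is not given.
- **Aplasia DLT (8.3.3).** Failure of ANC to reach 500/µL and of self-sustained platelets to reach 50,000/µL, judged "by treatment day +49 with no evidence of residual leukemia".
- **Response marrow (6.6).** At count recovery "or between Days +25 to +35 after start of G-CLAM chemotherapy, whichever occurs first".
- **Re-induction (6.6.2).** After CR with MRD, CRi or persistent disease, "patients are eligible for a second course of induction chemotherapy consisting of G-CLAM without decitabine". The condition is resolution of non-hematologic toxicity; no count level and no earliest day is stated.
- **Aplasia route (6.6.3).** "Patients with persistent aplasia without evidence of disease after Day +45" are removed from protocol.
- **After removal (8.4).** "patients will be monitored for late toxicities/complications for 1 month or until additional anti-AML therapy is given". Section 11.4 repeats this. Section 11.2.1 records the duration of cytopenias and reports an 8.3.3 event as a DLT.
- **Limits.** Section 14.2 accepts a dose at no more than 1 DLT in 6 and then no more than 3 in 12. Section 14.3 suspends at 7 or more in 19 and requires 13 or fewer in 41.

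**The concern.** A criterion read at Day +49 needs patients who can be read at Day +49. Section 14.1.2 asks only whether enough drug was given. A fully dosed patient whose marrow is read at, say, Day +30 can be called CRi and receive more chemotherapy with counts still low. Counts after that belong to Cycle 2, which 14.1.1 sets aside. The patient is not replaced, because the dose condition was met, and no Cycle 1 DLT is recorded.

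This bears on the toxicity the protocol itself singles out. The February 2018 update in Section 1.0 reports delayed or absent count recovery in 2 of 4 newly diagnosed patients given on-protocol consolidation, names MLFS as a concern, and says bone marrow aplasia will be added to the stopping rules. Section 8.3.3 is the DLT criterion that covers it. An unread status can only lower the DLT count, so every limit becomes easier to pass.

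**Working it through.** **1. The plan's own figure.** The exact (Clopper-Pearson) interval for 3 DLTs in 12 is 9.6% to 47.5% at 80% and 7.2% to 52.7% at 90%. Section 14.2 prints 10% to 48% and 7% to 53%. The table is reproduced, and it assumes that each of the 12 has a known DLT status.

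**2. Who can lack a valid Day +49 reading.**

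| Patient after Cycle 1 | Can 8.3.3 go unread? |
|---|---|
| Evident persistent leukemia | No. Residual leukemia excludes the event. |
| CR with MRD | No. Section 6.0 separates CR from CRi by count recovery, so counts have recovered. |
| CRi, counts already at or above 500 and 50,000 | No. Validly DLT-free under 8.3.3. |
| CRi, counts below those levels, new course before Day +49 | **Yes.** |
| Aplasia without disease, removed after Day +45 | Only if other anti-AML therapy starts before Day +49. |
| Death in aplasia before Day +49 from an infection exempt under 8.3.2 | **Yes.** Neither 8.3.2 nor a Day +49 reading captures it. |

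The CRi row is narrow. Section 6.0 needs only one lineage to be incomplete, while 8.3.3, read literally, needs both to be unrecovered.

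**3. Sensitivity of the limits.** One patient moves 1/6 to 2/6, 3/12 to 4/12, 6/19 to 7/19, or 13/41 to 14/41. Each step crosses a limit.

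**4. Illustration.** The documents give no Cycle 1 aplasia rate and no share unobserved, so both are assumptions. Let the true DLT rate be 40%, above the 33% ceiling in 14.1.3. Let *s* be the share of DLTs that are aplasia-only and *m* the fraction of those missed. The observed rate is p = 0.40 × (1 − s·m).

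- Phase 1 acceptance: Σ over x = 0, 1 of Bin(x; 6, p) × P(Bin(6, p) ≤ 3 − x).
- Both Phase 2 DLT limits: Σ over x = 0 to 6 of Bin(x; 19, p) × P(Bin(22, p) ≤ 13 − x), without conditioning on Phase 1.
- Phase 1 given the 1 DLT already seen in 6 (Section 1.0): P(Bin(6, p) ≤ 2).

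At p = 0.40, Phase 1 is 0.0467 × 0.8208 + 0.1866 × 0.5443 = 0.140.
With s = m = 1/4, p = 0.40 × (1 − 1/16) = 0.375, and Phase 1 is 0.0596 × 0.8535 + 0.2146 × 0.5960 = 0.179.

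| s | m | p | Phase 1 | Phase 1 given 1/6 | Both Phase 2 limits |
|---|---|---|---|---|---|
| any | 0 | 40% | 14.0% | 54.4% | 13.2% |
| 1/4 | 1/4 | 37.5% | 17.9% | 59.6% | 20.9% |
| 1/2 | 1/4 | 35% | 22.4% | 64.7% | 30.8% |
| 1/2 | 1/2 | 30% | 33.5% | 74.4% | 54.9% |

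The last two rows show how the effect grows with larger losses. They are not forecasts.

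**The case against.** The best defence is that the protocol already observes most of these patients. Four stronger readings are tempting, and the documents do not support them.

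- **Removal after Day +45 loses the Day +49 reading.** It does not by itself. Sections 8.4 and 11.4 continue monitoring for a month, 11.2.1 records cytopenia duration, and 6.5.1 suggests counts three times weekly until ANC passes 1,000/µL. Day +49 comes about four days after Day +45. Only new anti-AML therapy in that interval breaks the observation.
- **Every re-induced patient is an unread case.** The table above removes persistent disease, CR with MRD, and CRi patients already past the 8.3.3 levels. Aplasia without disease is routed to 6.6.3, not to re-induction.
- **Any death before Day +49 escapes.** Section 8.3.2 covers Grade 4 or higher non-hematologic toxicity, and the first cohort's early death was counted as a DLT. Only deaths from exempt infections remain.
- **A fifth to a third of all DLTs could be lost.** At 20% to 30% of all DLTs lost, Phase 1 acceptance would be 28.7% to 38.5% and passing both Phase 2 limits 44.9% to 64.7%. But only aplasia-only DLTs can be lost this way. If those are a quarter of DLTs, such a loss needs 80% to 120% of them to be missed, which is impossible at the top.

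It is also fair to say that the first six newly diagnosed patients were unaffected: one was already a DLT and the other five reached MRDneg CR. And 14.1.2 does not say in words how an unread status is scored. Non-DLT is the consequence of keeping the patient in the denominator with no event recorded.

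What stands is the missing observation condition. None of these safeguards supplies a Cycle 1 reading once new therapy has started.

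**Conclusion.** The concern holds for a limited group: chiefly CRi patients below the 8.3.3 thresholds who start new therapy before Day +49, plus aplastic patients given other anti-AML therapy before then and aplastic deaths from exempt infections. Followed as written, 14.1.2 keeps them in the denominator as non-DLTs. The bias has one direction, towards accepting the dose.

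Its size cannot be fixed from the documents. Under the modest assumption that aplasia-only events are a quarter of DLTs and a quarter of those are missed, a regimen with a true 40% DLT rate gains about 4 points of Phase 1 acceptance (14.0% to 17.9%) and about 8 points of passing both Phase 2 limits (13.2% to 20.9%). Given the 1 in 6 already observed, Phase 1 goes from 54.4% to 59.6%. The efficacy design (41 patients) is untouched. The plan should be amended because the gap concerns its own named toxicity, the limits turn on single patients, and the repair is cheap.

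**What to change.** - **Amend 14.1.2.** A patient is DLT-evaluable if a DLT occurred, or if at least 75% of doses were given and either recovery to the 8.3.3 thresholds was documented or counts were followed to Day +49 without new anti-leukemia therapy. State the Cycle 1 DLT window in days.
- **Report both counts.** For patients who start new therapy or die before Day +49 with counts below the thresholds and no evident leukemia, give the DLT rate with and without counting them as DLTs.
- **Apply the same rule** at 12, 19 and 41 patients.
- **Reconcile the text** on what follows a first course short of MRDneg CR. Section 1.0 takes these patients off study, Section 6.0 makes CRi eligible for consolidation after one course, 6.6.2 allows re-induction, and 6.8 ties consolidation after one course to MRDneg CR. Reconcile also Day +45 (6.6.3, 6.12.4) with Day +49 (8.3.3). No clinical rule is proposed here.

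**Cost.** Protocol wording, using counts and cytopenia durations that the plan already provides for. Reaching 12 evaluable patients takes 13 enrolled if 5% are unobserved (12/0.95 = 12.6) and 14 if 10% are (12/0.90 = 13.3), so possibly one or two replacements, or a slightly higher reported DLT rate.
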